4.0 STUDY ACTIVITIES AND ASSESSMENTS

The schedule of events is provided in Appendix 2. Descriptions of the scheduled evaluations are outlined below and complete information on study drug and dosing is provided in [Section 3.4](#).

4.1 DESCRIPTION OF PROCEDURES

4.1.1 Informed Consent

The subject must read, understand and sign the ICF approved by the institutional review board or independent ethics committee (IRB/IEC), confirming his or her willingness to participate in this study before initiating any screening activity that is not standard of care. Subjects must also grant permission to use protected health information, if required by local regulations.

4.1.2 Medical History

Collect and record the subject's relevant medical history through review of medical records and by interview. Concurrent medical signs and symptoms must be documented to establish baseline severities. A disease history, including the date of initial diagnosis and list of all prior systemic chronic GVHD treatments also will be recorded.

4.1.3 Adverse Events

The accepted regulatory definition for an AE is provided in Section 6.1. AEs will be recorded using CTCAE version 5.0 criteria. Important additional requirements for reporting SAEs are explained in Section 6.2.4.

4.1.4 Concomitant Medications and Therapy

Document all concomitant systemic medications and procedures from within 21 days before the start of study drug administration through 28 days after the last dose of study drug.

4.1.5 Confirmation of Eligibility

Subject eligibility for enrollment will be assessed per Section 3.3.1 and 3.3.2. All screening procedures, unless otherwise indicated, should be completed within 28 days of the first dose of study drug.

4.1.6 Karnofsky Performance Status

The Karnofsky performance index is provided in Appendix 5 and must be captured at enrollment to confirm eligibility.

4.1.7 Physical Examination, Vital Signs, Height & Weight

The screening physical examination will include, at a minimum, the height (screening only) and weight, blood pressure and general physical examination.

Symptom-directed and response assessment physical exams will be done during the treatment period and at the End of Study visit.

4.1.8 Serum Pregnancy Test

Pregnancy tests will be required for women of childbearing potential during screening.

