1.5.2 Safety Pharmacology

Glasdegib has been extensively characterized in nonclinical safety studies in rats, dogs and rabbits. Glasdegib was evaluated in safety pharmacology studies (cardiovascular, neurofunctional, respiratory), definitive toxicology assessments of up to 6- and 9-months duration, in vitro and in vivo genetic toxicity studies, local irritation study and embryo-fetal developmental toxicity studies. The primary target organs in rat included kidney, bone, and tooth. The primary target organs in the dog included kidney and liver. Additional observations of alopecia and skin irritation/inflammation, and QTc prolongation were identified in the dog.

In general, many findings in the rat and dog predict drug reactions reported in the clinic with glasdegib; these include muscle spasms, alopecia and QTc prolongation. However; not all the organ toxicities observed in animals have been observed in humans when treated with glasdegib. The kidney is a target organ in rat and dog. In the clinical program, at the 100 mg dose, acute kidney injury has been reported, primarily Grade 1-2. These events were often associated with prerenal confounders or consequent to or exacerbated by other glasdegib effects (e.g., diarrhea, vomiting, and/or decreased oral intake).

There have not been any liver events or significant increases in liver transaminases reported in the clinic. Findings in bone, teeth and testis are considered a potential concern only for pediatric patients, as Hh signaling is important in growth and development of these tissues. These effects have not been seen in adult patients and are not a risk for adults being treated with glasdegib.

Based on the available clinical data, the safety profile of glasdegib as a single agent administered orally on a once daily continuous dosing regimen is characterized by manageable and potentially reversible toxicities that are generally mild to moderate in severity. The key observed toxicities are: muscle spasms, dysgeusia, decreased appetite, and alopecia. Glasdegib can cause embryo-fetal death or severe birth defects when administered to a pregnant woman. Glasdegib is embryotoxic, fetotoxic, and teratogenic in animals.

For further details on the safety pharmacology of glasdegib, refer to the Investigator Brochure.

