3.4.2 Formulation, Packaging, and Storage

Glasdegib tablets will be provided by Pfizer Worldwide Research and Development from clinical supply. The study drug will be labeled and handled as open-label material, and packaging labels will fulfill all requirements specified by governing regulations. Glasdegib will be supplied as 25 mg tablets for oral administration.

Glasdegib will be packaged in high-density polyethylene bottles and should be handled with care. Each bottle will contain enough medication for the appropriate number of doses between study visits (one cycle worth dispensed at cycles 1-6, and three cycles' worth dispensed at cycles 7 and beyond), plus an additional amount to cover the allowed time windows around visit scheduling. Patients should be instructed to keep their medication in the bottles provided and not transfer it to any other containers and return the bottles to the site at the next study visit. Site personnel must ensure that patients clearly understand the directions for self-medication.

Investigational product should be dispensed by an appropriately qualified and experienced member of the study staff (e.g., physician, nurse, physician's assistant, practitioner, or pharmacist) as allowed by local, state, and institutional guidance.

Investigational glasdegib that will not be used (expired, returned, or leftover at end of study) should be destroyed on site according to the institution's standard operating procedure, and removal and destruction must be documented on drug accountability logs.

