3.9 PRECAUTIONS

3.9.1 Pregnancy Prevention

In this study, male subjects who are able to father children and female subjects who are of childbearing potential will receive glasdegib, a compound which has been associated with teratogenic risk. Subjects who are, in the opinion of the investigator, sexually active and at risk for pregnancy with their partner(s) must agree to use at least 1 highly effective form of contraception throughout the study and for at least 30 days after the last dose of investigational product. Male subjects must, additionally, use a condom to prevent potential transmission of investigational product in seminal fluid. The investigator or his or her designee, in consultation with the subject, will confirm that the subject has selected at least 1 appropriate method of contraception from the list of permitted contraception methods (see

Table 2 below) and will confirm that the subject has been instructed in its consistent and correct use. In addition, the investigator or designee will instruct the subject to call immediately if the selected contraception method is discontinued or if pregnancy is known or suspected in the subject or partner.

TABLE 2 Highly effective methods of contraception

Highly effective (failure rate <1 % if used consistently and correctly)	
Low user dependency	High user dependency

• Progestogen-only contraceptive implant• Intrauterine hormone releasing system (IUS)• Intrauterine device (IUD)• Bilateral tubal occlusion• Vasectomized partner	
• Combined hormonal contraception (estrogen and progestogen)
• Oral, intravaginal, transdermal, injectable• Progestogen-only hormonal contraception
• Oral, injectable

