3.10 DISCONTINUATION OF STUDY TREATMENT

The investigator may discontinue study treatment for any subject, if, in the investigator's opinion, it is not in the subject's best interest to continue. Additionally, a subject has the right to stop study treatment at any time. In addition, subjects may be withdrawn from study treatment for the following reasons:

- Study treatment should be discontinued if the drug is held for a treatment-related toxicity lasting > 28 days as defined above.
- Any subject who starts new systemic immunosuppressive therapy for the treatment of chronic GVHD, becomes pregnant, or is significantly noncompliant should stop study treatment.

The End of Treatment visit should occur 28 days after the last dose of study drug. Patients should be followed on the study schedule, every 3 months (see Section 3.0), unless they start a new systemic immunosuppressive treatment for cGVHD, relapse, or refuse to continue participation. Patients will continue to be followed by chart review for survival, relapse and cGVHD outcomes unless they withdraw consent.

Note that cGVHD progression itself does not require that subjects stop glasdegib unless a new systemic immune-suppressive medication is started. In some circumstances, investigators and subjects may want to continue glasdegib despite documented cGVHD progression if other options are not available.

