6.2.2 Assessment of Adverse Events

Investigators will assess the occurrence of AEs and SAEs at all subject evaluation timepoints during the study. All AEs and SAEs whether volunteered by the subject, discovered by study personnel during questioning, or detected through physical examination, or other means, will be recorded in the subject's medical record and on the AE CRF.

Each recorded AE or SAE will be described by its diagnostic term, duration (eg, start and end dates), severity, regulatory seriousness criteria, if applicable, suspected relationship to the study drug (see following guidance), and any actions taken. The relationship of AEs to the study drug will be assessed by means of the question: 'Is there a reasonable possibility that the event may have been caused by the study drug?' per FDA guidance on safety reporting requirements (FDA Guidance 2012).

See Appendix 8 for more detail on assessing relationship.

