6.2.3 Pregnancy, lactation, and occupational exposure

Even though there may not be an associated SAE, exposure to glasdegib during pregnancy, exposure during lactation, and occupational exposure are all reportable, and reporting procedures should follow those for SAEs.

All pregnancies and partner pregnancies that are identified during or after this study, wherein the estimated date of conception is determined to have occurred from the time of consent to 30 days after the last dose of study medication will be reported, followed to conclusion, and the outcome reported.

Subjects should be instructed to immediately notify the investigator of any pregnancies. Any female subjects receiving study drug who become pregnant must immediately discontinue study drug. The investigator should counsel the subject, discussing any risks of continuing the pregnancy and any possible effects on the fetus.

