Appendix 2. Schedule of Assessments

	SCR	C1D1	C1D8	C1D 15, 22	C2D1	C2D15	C3D1	C4D1	C5D1	C6D1	C7D1	C10D1, C13D1, C16D1, C19D1, C22D1	EOT
Visit Windows	-28 days	-7 days*	+/- 3 days			+/- 7 days							
Signed informed consent	X												
Confirm eligibility	X												
Physical exam and GVHD evaluation	X	X			X		X	X	X	X	X	X	X
Clinical labs ¹	X	X	X	X	X	X	X	X	X	X	X	X	X
Serum pregnancy test ²	X												
Electrocardiogram ⁵	X	X	X		X		X	X	X	X	X	X	
Research blood samples ⁵		X			X			X			X		
Skin biopsy		X										X	
Pulmonary function test		X											
Spirometry ⁵								X			X	X ⁴	X
Patient-reported outcomes ³		X						X			X	X	X
Chronic GVHD Provider Assessment		X			X		X	X	X	X	X	X	X
Dispense glasdegib study drug		X			X		X	X	X	X	X	X	

¹ Clinical labs to include CBC, ALT, AlkPhos, Total bilirubin, Creatinine, Sodium, Potassium, Magnesium. Verify that creatine kinase is normal prior to first dose.

² Serum pregnancy test required for women of childbearing potential **within -7 days of C1D1**.

³ Patient-reported outcomes to include: Lee Chronic GVHD Symptom Scale and PROMIS-29 (Appendix 10)

⁴ Spirometry required for cycles 10 and 13. Spirometry at cycles 16, 19, 22 is required only if a patient has BOS, otherwise as clinically indicated

⁵ Not required for patients who have discontinued glasdegib. (Spirometry is still required at EOT, unless it has already been done within the past 3 months.)

*Everything within this column can be done within the 7 days prior to the first dose, or on the actual Day 1. Do not need to repeat physical exam, clinical labs, or ECG if done within -7 days for screening. In all cases, study staff will check in with the patient by phone or in person within 48 hours prior to the first dose in order to confirm that there have been no significant changes to the patient's GVHD or overall health.

Target visit dates will be calculated based on a 28-day treatment cycle, and with C1D1 as the starting date.

End of Treatment (EOT) visit should occur 28 days (+/- 7 days) from last dose of study drug.

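### No pregnancy test is scheduled after the first dose of a drug the protocol says can cause embryo-fetal death or severe birth defects, with treatment lasting up to 24 cycles

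*Combined protocol and SAP*

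**What the plan says.** The two places that govern pregnancy testing agree. Section 4.1.8 states: "Pregnancy tests will be required for women of childbearing potential during screening". In Appendix 2 the serum pregnancy row has a single mark, under screening, and its footnote reads "Serum pregnancy test required for women of childbearing potential", with the timing set at within 7 days before C1D1. The clinical laboratory panel (Section 4.1.10 and Appendix 2, footnote 1) contains no pregnancy test.

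On the hazard, Section 1.5.2 states: "Glasdegib can cause embryo-fetal death or severe birth defects when administered to a pregnant woman".

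On what follows a pregnancy, Section 6.2.3 states: "Any female subjects receiving study drug who become pregnant must immediately discontinue study drug". Section 3.10 likewise says that a subject who "becomes pregnant, or is significantly noncompliant should stop study treatment".

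On prevention, Section 3.3.1 admits women of childbearing potential who agree to highly effective contraception, or to abstinence or exclusively non-heterosexual activity. Section 3.9.1 says that sexually active subjects at risk of pregnancy "must agree to use at least 1 highly effective form of contraception throughout the study" and for at least 30 days after the last dose. They are also told to call if the method is stopped or a pregnancy is suspected. Section 6.2.2 adds: "Investigators will assess the occurrence of AEs and SAEs at all subject evaluation timepoints during the study".

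On drug supply, Section 3.4.2 dispenses one cycle at a time through cycle 6 and three cycles at a time from cycle 7, "plus an additional amount to cover the allowed time windows around visit scheduling".

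**The concern.** The plan names a severe harm, admits women who could suffer it, and orders drug stopped at once if pregnancy occurs. It schedules nothing after the first dose that is designed to detect a pregnancy. If contraception fails, an early pregnancy without symptoms could continue under daily dosing until the woman suspects it. The stop rules in Sections 3.10 and 6.2.3 can act only from that point. The reporting duty in Section 6.2.3 covers conceptions up to 30 days after the last dose, and it too depends on the pregnancy being identified.

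The stake is patient safety alone. The timing of the screening test is clear and is not in question, and no endpoint, analysis or stopping boundary is touched.

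**Working it through.** There is no plan figure to reproduce. The check is a count from Appendix 2 and some day arithmetic.

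**Inputs from the documents**
- Maximum treatment: 24 cycles (Section 3.0). This is a ceiling, since duration depends on tolerability and response (Section 3.6).
- Cycle length: 28 days (Appendix 2).
- Dispensing visits after C1D1: C2D1 to C7D1, C10D1, C13D1, C16D1, C19D1 and C22D1, which is 6 + 5 = 11 (Appendix 2).
- EOT: 28 days (+/- 7) after the last dose (Appendix 2).
- Contraceptive failure: below 1% with consistent and correct use, no time unit given (Section 3.9.1).

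**Tests against visits.** Appendix 2 lists 16 visits after C1D1: C1D8, C1D15, C1D22, C2D1, C2D15, C3D1, C4D1, C5D1, C6D1, C7D1, C10D1, C13D1, C16D1, C19D1, C22D1 and EOT. Clinical labs are drawn at all 16; pregnancy tests at none.

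**Dosing after the only test**
- Maximum: 24 x 28 = 672 days, or 672 / 365.25 = 1.84 years.
- From C7D1: (24 - 6) x 28 = 504 days; 504 / 672 = 75%.

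**Gaps if tests are added at the 11 dispensing visits and EOT (12 tests)**
- First dose through C7D1: nominally 28 days.
- After C7D1: 3 x 28 = 84 days, or 84 + 7 + 7 = 98 days if one visit is a week early and the next a week late. Section 3.4.2 supplies drug to cover such windows.
- C22D1 to EOT: 84 + 28 = 112 days, of which 84 are dosing days.

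**Gaps if home tests are also done at the 12 cycle starts without a visit** (C8, C9, C11, C12, C14, C15, C17, C18, C20, C21, C23, C24)
- Between tests during dosing: nominally 28 days throughout.
- C24D1 to EOT: 28 + 28 = 56 days, of which only the first 28 are dosing days.

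**Expected number of pregnancies (illustration).** The documents do not say how many of the 20 subjects will be women of childbearing potential. Assume 1 to 8, all treated for the full 1.84 years, with 1% failure per woman-year:
- 1 woman: 1 x 1.84 x 0.01 = 0.018
- 8 women: 8 x 1.84 x 0.01 = 0.147

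If no such woman enrols, the count is zero. Shorter treatment or a failure rate under 1% lowers it; imperfect use raises it.

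**The case against.** The strongest reply is that this is a layered design choice and not an error. A positive serum test excludes (Section 3.3.2). Effective contraception or abstinence is mandatory, the investigator confirms the method and instruction in its use, and subjects must call if it lapses. Adverse events are assessed at every visit, there is telephone follow-up after the last dose (Section 4.3), and a known pregnancy stops treatment. Nothing in the documents sets a testing interval that the plan breaks. The subgroup may be empty and the expected count is far below one.

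Much of this stands. The plan does not contradict itself, the probability is low, and the count above is only an illustration. But each safeguard during treatment depends on adherence or suspicion. Section 3.9.1 ties its failure rate to consistent and correct use and permits methods that it classes as highly user dependent. Adverse-event questioning and symptom-directed examination (Section 4.1.7) may reveal a pregnancy but are not designed to find an early one without symptoms. Nor does low probability settle the matter on the protocol's own practice: Section 1.6.3.2 calls QT prolongation unlikely and still monitors ECGs.

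Two objections to the remedy are fair. Testing only at dispensing visits leaves 84-day gaps in the phase that holds 75% of maximum dosing; home tests are needed to close them. And an EOT test, which may fall as early as day 21 after the last dose, cannot exclude a conception late in the 30-day reporting window. These limit what testing can achieve; they do not argue for having none.

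**Conclusion.** The concern holds. The body text and the schedule agree on one pregnancy test, before the first dose, with up to 672 dosing days after it. The stop-on-pregnancy rule therefore has no scheduled detection step behind it.

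The likely number of events is small: about 0.02 to 0.15 in the whole trial if 1 to 8 women of childbearing potential are treated to the maximum at 1% failure per year, and zero if none enrol. The case rests on the severity of the harm named in Section 1.5.2 and the low cost of the remedy, not on frequency. Testing would detect a pregnancy sooner; it would not prevent one. This is a change the sponsor should make, but the validity of the trial does not depend on it. The Investigator Brochure and Manual of Operations were not available, so the conclusion concerns the protocol and its schedule.

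**What to change.** Amend Section 4.1.8 and Appendix 2 so that women of childbearing potential have a pregnancy test, on blood already drawn and before drug is dispensed, at C2D1 to C7D1, C10D1, C13D1, C16D1, C19D1 and C22D1, and again at EOT. Where the EOT visit is not held, as Section 4.3 allows, obtain a home urine test result by phone about 28 days after the last dose.

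As an optional addition, have a home urine test done at the start of each of the 12 cycles without a visit. This brings the nominal interval during dosing back to 28 days.

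The cost is a schedule amendment and at most 11 + 1 = 12 assays per affected woman, with no extra visit. The optional step adds at most 12 urine kits and phone checks per woman. The downsides are the small assay cost and an occasional false positive that needs a repeat test.

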4.1.9 Hematology

Hematology studies must include complete blood count (CBC) with differential, including hemoglobin, hematocrit, platelet count, and ANC.

4.1.10 Serum Chemistry

Chemistry panel must include alkaline phosphatase, ALT, creatinine, total bilirubin, sodium, potassium, magnesium.

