3.3 SELECTION OF STUDY POPULATION

3.3.1 Inclusion Criteria

Eligible subjects will be considered for inclusion in this study if they meet **all** of the following criteria:

1. At least 18 years old
2. Diagnosed with moderate or severe cGVHD according to the 2014 NIH Consensus Criteria
3. Diagnosed with cGVHD-related sclerosis or fasciitis
 - Skin feature score of at least 2 OR
 - Joints and fascia score of at least 1
4. New, stable or progressive sclerosis/faciitis despite treatment with at least one prior line of systemic therapy for cGVHD.
5. Female patients who:
 - Are documented to be postmenopausal or are surgically sterile, OR

- If of childbearing potential, agree to use at least 1 highly effective method of contraception from the time of signing the informed consent form through 30 days after the last dose of study drug, OR agree to practice true abstinence or exclusively non-heterosexual activity when this is in line with the preferred and usual lifestyle of the subject

6. Male patients who:

- Are surgically sterile (vasectomized) OR
- Agree to use at least 1 highly effective method of contraception during the entire study treatment period and through 30 days after the last dose of study drug, OR agree to practice true abstinence or exclusively non-heterosexual activity when this is in line with the preferred and usual lifestyle of the subject, AND
- Agree to use a condom to prevent potential transmission of investigational drug in seminal fluid

7. Patients who meet the following clinical laboratory criteria:

- Absolute neutrophil count (ANC) >1000/ μ L, platelet count >50 \times 10⁹/mL
- ALT and AST < 2x ULN and normal total bilirubin unless attributed to cGVHD
- Creatinine < 2.0 mg/dL

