3.4.3 Administration of Study Drug

Glasdegib will be administered at a dose of 50 mg once daily by mouth. Up to 24 months of glasdegib treatment will be administered on study. Glasdegib is 77% bioavailable with a time to peak concentration of less than 2 hours. The drug is metabolized through the CYP3A4 pathway with a half life of 17 hours. Steady state is reached after 8 days.

At any time, patients may hold glasdegib because of side effects, toxicity or for logistic reasons. Any number of doses may be held as long as drug is resumed within 28 days. If glasdegib is held for longer than 28 days, it should not be restarted and the patient is just followed for clinical endpoints.

All protocol-specific criteria for administration of study drug must be met and documented before drug is started. Study drug will be administered or dispensed under the supervision of the investigator or identified sub-investigators. Subjects should be monitored for toxicity, and doses of glasdegib should be modified as needed to accommodate subject tolerance to treatment.

Glasdegib will be self-administered by the patient at home, unless otherwise specified. Glasdegib will be administered orally with approximately 8 ounces (240 mL) of water and should be taken in the morning, at the same time each day with or without food. Tablets must not be crushed or cut; they must be swallowed whole, not manipulated or chewed prior to swallowing. Patients should be instructed to not to take more than the prescribed dose at any time. If a patient forgets to take their dose at the regularly scheduled time, and if less than 10 hours have passed since the scheduled dosing time, that dose should be taken as soon as possible. If more than 10 hours have passed since the scheduled dosing time, the dose should be skipped and the patient should continue on their normal dosing schedule. If a patient misses a day's dose entirely, they must be instructed not to "make it up" the next day. If a patient vomits any time after taking a dose, they must be instructed not to "make it up," but to resume subsequent doses the next day as prescribed. If a patient inadvertently takes 1 extra dose during a day, the patient should not take the next dose of glasdegib.

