6.2.4 Hy's Law Cases

Cases of potential drug-induced liver injury as assessed by laboratory values are also reportable to Pfizer as SAEs. If a study subject develops abnormal values in AST and/or ALT, concurrent with abnormal elevations in total bilirubin and no other known cause of liver injury, that event is classified as a Hy's Law Case and must be reported.

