Appendix 7. Response Determination

Response determination for chronic GVHD clinical trials based on clinician assessments

Organ	Complete Response	Partial Response	Progression
Skin	NIH Skin Score 0 after previous involvement	Decrease in NIH Skin Score by 1 or more points	Increase in NIH Skin Score by 1 or more points, except 0 to 1
Eyes	NIH Eye Score 0 after previous involvement	Decrease in NIH Eye Score by 1 or more points	Increase in NIH Eye Score by 1 or more points, except 0 to 1
Mouth	NIH Modified Oral Mucosa Rating Score 0 after previous involvement	Decrease in NIH Modified Oral Mucosa Rating Score of 2 or more points	Increase in NIH Modified Oral Mucosa Rating Score of 2 or more points
Esophagus	NIH Esophagus Score 0 after previous involvement	Decrease in NIH Esophagus Score by 1 or more points	Increase in NIH Esophagus Score by 1 or more points, except 0 to 1
Upper GI	NIH Upper GI Score 0 after previous involvement	Decrease in NIH Upper GI Score by 1 or more points	Increase in NIH Upper GI Score by 1 or more points, except 0 to 1
Lower GI	NIH Lower GI Score 0 after previous involvement	Decrease in NIH Lower GI Score by 1 or more points	Increase in NIH Lower GI Score by 1 or more points, except from 0 to 1
Liver	Normal ALT, alkaline phosphatase, and Total bilirubin after previous elevation of one or more	Decrease by 50%	Increase by 2x ULN
Lungs	-Normal %FEV1 after previous involvement -If PFTs not available, NIH Lung Symptom Score 0 after previous involvement	-Increase by 10% predicted absolute value of %FEV1 -If PFTs not available, decrease in NIH Lung Symptom Score by 1 or more points	-Decrease by 10% predicted absolute value of %FEV1 -If PFTs not available, increase in NIH Lung Symptom Score by 1 or more points, except 0 to 1
Joints and Fascia	Both NIH Joint and Fascia Score 0 and P-ROM score 25 after previous involvement by at least one measure	Decrease in NIH Joint and Fascia Score by 1 or more points or increase in P-ROM score by 1 point for any site	Increase in NIH Joint and Fascia Score by 1 or more points or decrease in P-ROM score by 1 point for any site
Global	Clinician overall severity score 0	Clinician overall severity score decreases by 2 or more points on a 0–10 scale	Clinician overall severity score increases by 2 or more points on a 0–10 scale

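### The Hy's Law reporting rule accepts an abnormal AST, but the required laboratory panel includes no AST at any visit after the first dose

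*Combined protocol and SAP*

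**What the plan says.** Section 6.2.4 (Hy's Law Cases) opens with the reporting duty: "Cases of potential drug-induced liver injury as assessed by laboratory values are also reportable to Pfizer as SAEs". The definition then begins "If a study subject develops abnormal values in AST and/or ALT" and adds a concurrent rise in total bilirubin with no other known cause of liver injury. Either enzyme is enough for the transaminase part, and no multiple of the upper limit of normal is set.

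The tests that sites must run are listed in two places:

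- Section 4.1.10 (Serum Chemistry): "Chemistry panel must include alkaline phosphatase, ALT, creatinine, total bilirubin, sodium, potassium, magnesium".
- Appendix 2, footnote 1, which defines the clinical laboratory row of the visit schedule: "Clinical labs to include CBC, ALT, AlkPhos, Total bilirubin, Creatinine, Sodium, Potassium, Magnesium".

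The two lists agree on the liver tests: ALT, alkaline phosphatase and total bilirubin.

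Apart from the abbreviation list and Section 6.2.4, AST is named only in inclusion criterion 7 (synopsis and Section 3.3.1): "ALT and AST < 2x ULN and normal total bilirubin unless attributed to cGVHD". Section 4.1.5 says "Subject eligibility for enrollment will be assessed per Section 3.3.1 and 3.3.2", and Section 3.4.3 says "All protocol-specific criteria for administration of study drug must be met and documented before drug is started".

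**The concern.** A mandatory reporting rule should rest on mandatory data. Here one of the two enzymes that can trigger the rule is not required at any visit after treatment starts. Whether an AST-only case is found then depends on whether the local laboratory at each of the 3 centers happens to run AST.

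Two features of the trial give the gap some weight. Safety and tolerability are the primary endpoint (Section 5.5.2.1), and Section 1.6.1 states that there are no reports of glasdegib use in chronic GVHD. In addition, the toxicity stopping rule in Section 3.12 lists raised transaminases of grade 3 or higher among the known reactions that count towards halting enrollment. A grade 3 AST rise with a lower-grade ALT would not be seen by that rule at a site running only the required panel.

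**Working it through.** There is no figure in the plan to reproduce. The check compares the analytes the rule needs with those the schedule requires, and then counts the draws affected.

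**Step 1. Where AST is required**

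| Place in the document | ALT | AST | Total bilirubin |
|---|---|---|---|
| Inclusion criterion 7 (Section 3.3.1) | yes | yes | yes |
| Minimum chemistry panel (Section 4.1.10) | yes | no | yes |
| Scheduled clinical labs (Appendix 2, footnote 1) | yes | no | yes |
| Hy's Law definition (Section 6.2.4) | yes | yes | yes |
| Liver response (Appendix 7) | yes | no | yes |

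Before treatment, an AST value is implied even though the panel omits it: criterion 7 sets a limit on AST, Section 4.1.5 requires eligibility to be assessed against that criterion, and Section 3.4.3 requires criteria to be met and documented before dosing. After the first dose nothing plays this role.

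**Step 2. Which cases the required panel can detect**

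Take a patient on treatment with raised bilirubin and no other known cause of liver injury.

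| ALT | AST | Meets Section 6.2.4 | Detectable from required labs |
|---|---|---|---|
| abnormal | abnormal | yes | yes |
| abnormal | normal | yes | yes |
| normal | abnormal | yes | **no** |
| normal | normal | no | not applicable |

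Only the third row is affected. Because Section 6.2.4 has no fold threshold, even a modest AST rise puts a patient in that row.

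**Step 3. How many draws are affected**

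The clinical laboratory row of Appendix 2 is marked in all 13 columns. Expanding the two grouped columns gives:

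- Before or at the first dose: screening and C1D1 = 2.
- After the first dose: C1D8, C1D15, C1D22, C2D1, C2D15 (5); C3D1, C4D1, C5D1, C6D1, C7D1 (5); C10D1, C13D1, C16D1, C19D1, C22D1 (5); EOT (1). Total 5 + 5 + 5 + 1 = 16.
- All time points: 2 + 16 = 18.

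ALT and total bilirubin are required at 16 of the 16 time points after the first dose; AST is required at 0 of 16. With the planned 20 patients, the upper bound is 20 × 16 = 320 draws without a required AST.

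**Step 4. Whether efficacy is touched**

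Complete response in the liver is defined in Appendix 7 as "Normal ALT, alkaline phosphatase, and Total bilirubin after previous elevation of one or more". AST does not enter it, so the response endpoints are unaffected.

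**The case against.** The strongest reply is that nothing in the plan is contradictory. Section 6.2.4 is a reporting rule, not a monitoring schedule. Since either enzyme suffices, the rule works on the required ALT and bilirubin, and AST merely extends it to values a site happens to hold. The panel is a minimum that sites may exceed. A missed case also needs several things at once: abnormal AST, normal ALT, raised bilirubin and no other cause. Bilirubin is measured at every one of these visits, and a new unexplained rise would normally be worked up. Section 3.7 asks for close follow-up of laboratory abnormalities, and Section 6.2 collects laboratory changes that lead to intervention or are judged clinically significant. The background is reassuring too: Section 1.5.2 reports no liver events or significant transaminase increases in the clinic, and Section 1.6.2 says liver toxicity has not been identified as drug-related. Finally, 320 counts draws under full attendance. Patients who stop early skip interim monthly visits (Section 3.0), and the EOT visit is waived in some circumstances (Section 4.3).

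Much of this stands. It limits the consequence and shows that 320 says nothing about the number of missed cases. It does not make AST required at any visit after the first dose. A bilirubin rise may prompt a clinician to order AST, but the protocol does not compel it, so ascertainment of this kind of case is left to local habit.

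**Conclusion.** The concern holds. On the text alone, AST qualifies a patient for a mandatory report under Section 6.2.4 and is required at none of the 16 scheduled laboratory time points after the first dose (at most 320 draws across 20 fully attending patients).

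The consequence is small and limited to safety. It is confined to cases with abnormal AST, normal ALT and raised bilirubin, plus any grade 3 or higher AST rise without a matching ALT rise that should have counted in the Section 3.12 toxicity rule. The number of such cases cannot be estimated from the documents and is probably low. For a case to be missed, the site must run only the required panel and must not order AST when bilirubin rises; the documents do not show how often that would happen. Confidence is high that AST is omitted; no claim is made about how many cases would be lost. This is a worthwhile improvement rather than a flaw that threatens the trial's conclusions.

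**What to change.** Add AST to the chemistry panel in Section 4.1.10 and to footnote 1 of Appendix 2. The Hy's Law rule can then be applied in full at every scheduled draw, AST rises become visible to the transaminase part of the stopping rule, and the pre-treatment AST needed for inclusion criterion 7 is listed explicitly instead of being inferred from three other sections.

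The cost is one extra analyte on blood already being drawn and two lines of wording. No visit is added, and the sample size, stopping boundaries and analyses stay as they are.
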